A clinical trial to validate an automated online language interpreting tool with Hispanic patients who have limited English proficiency – Phase Two.

1) Protocol Title

A clinical trial to validate an automated online language interpreting tool with Hispanic patients who have limited English proficiency – Phase Two.

Funded by AHRQ. R01 HS024949 2016-2021

Protocol Version Date: 4-3-2019

2) Objectives

This is the second stage (years 2 through 4) of a 5-year project funded by AHRQ. This stage analyzes video recorded data from new recruitment of patients — in addition to videos to be analyzed from the UCD IRB approved clinical trial 522696 “A controlled trial of Patient Centered Telepsychiatry Interventions.” This stage constitutes a clinical trial of the automated online language interpreting tool developed by us in 2016/17.

In this randomized cross-over study with patient recruitment occurring during years 2 through 4, up to 100 Spanish speaking patients will be recruited from several outpatient clinics in Sacramento, and will receive two psychiatric interviews: Method A (conventional in-person interview with a psychiatrist with a live human interpreter) and Method B (asynchronous telepsychiatry — that is, video-recorded interviews that are subsequently processed with automated speech recognition and machine translation technologies). 80 of these patients will have a previous psychiatric diagnosis, and 20 of the 100 patients will have no previously-diagnosed psychiatric disorders, but a chronic medical condition.

In addition to this interview, the patient will complete a battery of questionnaires and a Spanish version of the Structured Clinical Interview for DSM (SCID)^{i,iii}. Both clinical interviews will be digitally video recorded for comparative analysis of language and translation accuracy, as well as for repeat diagnostic and inter-rater reliability assessments by Spanish and English speaking psychiatrists in year 5. Patients and assessing psychiatrists will all be enrolled as subjects.

3) Background

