There is a pressing national need to provide higher-quality, more effectively accessible language interpretation services to improve the health outcomes of the 4.7% of the US population who have limited English proficiency (LEP)ⁱⁱⁱ and who currently, as a result, have increased rates of hospital admissions, misdiagnosis, improper treatment and poorer health comprehension and outcomes.^{iv} This project addresses a critical component of this problem: the need to improve access to high quality, mental health services for diverse populations by improving the flow of clinical work across care settings (primary care and specialty care) through the use of online asynchronous methods of communicating. We have already created and demonstrated an efficient, provider compatible, administratively simple health IT solution: Asynchronous Telepsychiatry (ATP). We are now building an automated language translation process into our ATP consultations to allow clinical evaluations to occur across languages without the use of human interpreters.

An 8-minute summary of our past work leading to this study is on YouTube at https://www.youtube.com/watch?v=g8_5hCF2q6I.

A clinical trial to validate an automated online language interpreting tool with Hispanic patients who have limited English proficiency – Phase Two.

In this study, after completing the first phase of tool development and testing, we plan to compare two methods of cross-language psychiatric assessment:

- Method A (current gold standard of in-person real-time interpreting practice). A Spanish-speaking patient is diagnostically assessed in-person by an English-speaking psychiatrist through a Spanish-speaking interpreter.
- Method B (comparative practice – ATP).^{v,vi,vii,viii,ix,x,xi} A Spanish-speaking patient is interviewed in Spanish by a trained mental health interviewer. The interview is recorded in real time, translated into English with sub-titles added to the video file, and sent to an English-speaking psychiatrist to asynchronously — that is, at a later time — review the video and make a diagnosis.

All patients will undergo evaluation by both methods. Half of the patients will be randomized to be assessed by Method A first, followed by Method B and half to be assessed by Method B first, followed by Method A. The specific aims of the study are:

- *Aim 1:* To iteratively evaluate and refine the automated asynchronous interpretation tool already developed in prior studies.

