Method A (current gold standard of in-person real-time interpreting practice). A Spanish-speaking patient is diagnostically assessed in-person by an English-speaking psychiatrist through a Spanish-speaking interpreter. A report with treatment recommendations following American Psychiatric Association guidelines will be sent, with the consent of the patient, to the PCP or treating psychiatrist who will be able to have ad-lib telephone or e-mail consultations with the psychiatrist ([name] - Provider A) at UCDHS (consistent with the UCDHS services to community providers). [name] will have access to all previous clinical information about the patients. This entire interview will be video-recorded for comparison purposes and data analysis

A clinical trial to validate an automated online language interpreting tool with Hispanic patients who have limited English proficiency – Phase Two.

later and will be the clinical interview that is used as a psychiatric consultation for the PCP's to use to assist in follow-up treatment of their patients.

[figure not shown]

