Method B (comparative practice – ATP).^{vvi,vii,viii,ix,x,xxvi,xxvii,xxviii} A Spanish-speaking patient is interviewed in Spanish by a trained mental health interviewer. This interview will be conducted by a bilingual Licensed Professional Counselor (LPC), Nurse Practitioner (NP) or a Licensed Clinical Social Worker (LCSW), Marriage and Family Therapist (MFT) or Licensed Trainee under supervision (provider B), whom we will employ. The interview is video-recorded in real-time, automatically translated into English with sub-titles added to the video file, and sent to [name] (provider C) and to 3 English-speaking psychiatrists (Provider D) to asynchronously review the video and make a diagnosis. This interview will be video-recorded. The interviewers will then fill out a standardized clinical template that will be reviewed at the end of the study for comparison and data analysis. This interview will not be used for clinical purposes during the study. At the conclusion of the interviews patients will be given a release of information to self or a release of information to their pcp to sign, if they wish to receive the research psychiatric recommendations or have them sent to their pcp. All patients will be diagnostically assessed by [name] (provider A) who is non-Spanish speaking (who will interview for method A). All video-recordings of both methods for all patients will be reviewed by [name] (provider C), who is Spanish speaking, and he will ensure that there are no major language related errors in [name] reports to the PCP's that are based on method A. If [name] (Provider C) believes language interpretation has caused an error by [name] in method A, the two psychiatrists will discuss the issue and arrive at a consensus recommendation for the PCPs, and we will note this as part of our analysis.

Data Analysis:

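### Aim 3: Spanish-speaking Provider C's Method B diagnoses need not depend on the translation or be independent of Method A, and their place in accuracy and kappa is not stated

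*Combined protocol and SAP*

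**What the plan says.** The Background section (3) describes Method B as a Spanish interview that is recorded, subtitled in English and "sent to an English-speaking psychiatrist to asynchronously" diagnose at a later time. The Method B text in section 7 has a wider set of readers: the video is "sent to [name] (provider C) and to 3 English-speaking psychiatrists (Provider D) to asynchronously review the video and make a diagnosis".

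The same paragraph gives Provider C further tasks. "All video-recordings of both methods for all patients will be reviewed by" Provider C, "who is Spanish speaking, and he will ensure that there are no major language related errors" in Provider A's Method A reports. If C thinks interpretation has caused an error, "the two psychiatrists will discuss the issue and arrive at a consensus recommendation for the PCPs". Provider A, for Method A, "will have access to all previous clinical information about the patients".

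On the use of the reads, the Objectives section (2) says both interviews are recorded for, among other things, "repeat diagnostic and inter-rater reliability assessments by Spanish and English speaking psychiatrists in year 5". Section 6 names kappa for diagnostic accuracy and inter-rater reliability but names no reader pairs. The visible Data Analysis text in section 7 gives specifics for Aim 2 only. The figures, including Figure 1, are not shown in the text available.

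**The concern.** Aim 3 compares the diagnostic accuracy and reliability of the two methods. For Method B, the new element is the machine translation. A reader who understands the Spanish audio can reach the right diagnosis when the subtitles are wrong, so that read is not a test of the subtitles.

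C's reads may also fail to be independent of Method A. C sees the same patient's other interview, reads A's report and may discuss the case with A, who has the prior clinical record. With no stated order, C's Method B diagnosis can be made with that knowledge in hand.

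Because C's analytic role is open, someone could decide after seeing the data which reads make up Method B accuracy and which pairs make up each kappa. The result could depend on that choice.

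**Working it through.** The plan states no sample size, accuracy or kappa for Aim 3, so there is no figure of its own to reproduce. The Aim 2 power statement is not in dispute. From the documents: three D readers, one C reader, 100 patients. Everything else below is assumed, for illustration: a binary diagnosis, each reader 85% accurate when the language is understood, C relying wholly on the audio, and subtitles that reverse the diagnosis in a fraction e of videos (20%, range 10–30%).

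**Accuracy.** If four reads were averaged equally and only the three D reads suffered a loss L, the average would lose 3L/4 = 0.75L.

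D accuracy = 0.85(1−e) + 0.15e. The four-read mean = (3D + 0.85)/4.

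| e | D accuracy | Four-read mean |
|---|---|---|
| 0.10 | 78.0% | 79.8% |
| 0.20 | 71.0% | 74.5% |
| 0.30 | 64.0% | 69.3% |

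At e = 0.20 the true loss is 14 points and the pooled figure shows 10.5.

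**Kappa.** Four readers form six pairs, three of which include C. Take 50% prevalence and e = 0.20.

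- Subtitle errors shared by all D readers: two D readers are reversed together, so they agree in 0.85² + 0.15² = 0.745 of cases and D-D kappa = (0.745 − 0.5)/0.5 = 0.49. A C-D pair agrees in 0.8 × 0.745 + 0.2 × 0.255 = 0.647, so kappa = 0.29. The six-pair mean is 0.39. Including C lowers kappa.
- Same D accuracy of 71%, but with reader-specific errors: D-D = (0.71² + 0.29² − 0.5)/0.5 = 0.18; C-D = (0.85 × 0.71 + 0.15 × 0.29 − 0.5)/0.5 = 0.29; mean 0.24. Including C raises kappa.

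Nor does D-D kappa alone track accuracy. At 80% prevalence with shared errors it goes from 0.38 (e = 0) to 0.46 (e = 0.20) while D accuracy falls from 85% to 71%. If instead the subtitles affect only true negatives (20% of them), D-D kappa falls from 0.38 to 0.34. There is no fixed direction.

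**Cost of leaving C out of the accuracy average.** If all four reads were equally correlated (r), the standard error ratio of three to four reads is √{[(1+2r)/3]/[(1+3r)/4]}: 1.15 at r = 0 and 1.01 at r = 0.8, an increase of 1–15%.

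In the shared-error illustration at e = 0.20, both of two D reads are correct with probability 0.8 × 0.85² + 0.2 × 0.15² = 0.5825. Their correctness correlation is (0.5825 − 0.71²)/(0.71 × 0.29) = 0.381, and their correlation with C is 0. Then:

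- D-only SE = √[0.2059 × (1 + 2 × 0.381)/3/100] = 3.48 points.
- Pooled SE = √[(9 × 0.1209 + 0.1275)/16/100] = 2.76 points. The ratio is 1.26.
- Pooled bias is 3.5 points, so pooled total error = √(2.76² + 3.5²) = 4.46 points, against 3.48 for D only.

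Repeating this for smaller e, D-only SE against pooled total error is 2.94 vs 2.95 points at e = 0.10, 2.56 vs 2.29 at 0.05, and 2.28 vs 1.96 at 0.02. Below about 10% of videos affected, pooling has the smaller total error.

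**The case against.** The strongest reply is that the plan does give these reads a purpose. The Objectives section openly includes Spanish-speaking psychiatrists in the year-5 reliability work, and section 6 names kappa. That stands: a reader might infer that C's reads have no stated use, and the documents do not support that. Only C's place in the accuracy and kappa estimates is missing, and the figures not shown might say something about it.

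A reader might also infer that the plan pools C with D. It does not propose this, and the 0.75 factor is conditional on equal averaging and on C relying on the audio. The numerical inputs are assumed, and the SCID gives primary and secondary diagnoses rather than one binary result. The Background wording does not exclude a bilingual psychiatrist, so D-only accuracy is a choice of estimand, and one with larger total error when few videos are affected. These points stand and limit what the illustration can show.

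It is tempting to go further and say that A and C form the only Method A pair. Section 7 says C reviews Method A recordings and checks reports; it does not say C makes a Method A diagnosis, and the year-5 reads may supply other pairs.

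Finally, C's report check protects advice going to primary care, while Method B video must first be processed. Where the check comes first, an earlier Method B diagnosis is not possible; where it comes second, C's Method A review is informed by Method B. This limits what ordering can achieve. It does not remove the need to record the order.

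**Conclusion.** The concern holds for Aim 3. As written, the plan yields Method B diagnoses from Provider C that need not depend on the subtitles and may be contaminated by Method A, and the visible text does not say whether they count towards Method B accuracy and kappa. The possible distortion of accuracy is a quarter of any translation-caused loss (3.5 points at an assumed 20% of videos), but only under equal pooling and full reliance on the audio. The effect on kappa has no predictable sign.

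The trial as a whole is not undermined: the three D reads and the Aim 4 error scoring still test the tool directly. Nor is Aim 2 defective. A reader might object that patients speak Spanish directly and rate their satisfaction after each interview, whereas Method B consists of "video-recorded interviews that are subsequently processed with automated speech recognition and machine translation technologies", so their ratings cannot register the translation. But Aim 2 claims only to compare satisfaction with the two methods, and interpretation quality is assigned to Aim 4. It is enough to note that conclusions about the translation tool rest on Aims 3 and 4.

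**What to change.** 1. State C's role in Aim 3. Base Method B accuracy against the SCID on the three Provider D reads, in line with the English-speaking reader in the Background section.
2. Report C's Method B read separately as a language-concordant benchmark. Show D-D and C-D kappa side by side, and label every pair that includes a Spanish speaker.
3. Have C record and time-stamp the Method B diagnosis before viewing that patient's Method A material, where the planned report check allows. Leave that check unchanged and log the viewing order. If a Method A kappa uses C, use diagnoses recorded before any discussion between A and C.

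The cost is analysis-plan wording, time stamps and a viewing log; items 1 to 3 need no new Method B reads. A Method A kappa that uses C would need C's Method A diagnosis to be recorded. The standard error of Method B accuracy rises by 1–15% if reads are equally correlated (assumed), or about 26% in the 20% illustration. If fewer than about 10% of videos are affected in that illustration, total error is larger than with pooling, and the gain is then a clearer meaning rather than precision.

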- *Aim 2:* To compare patient satisfaction of Method A vs. Method B.
- *Aim 3:* To compare the diagnostic accuracy and psychiatrist inter-rater reliability of Method A vs. Method B and demonstrate psychiatrist inter-rater reliability for Method B.
- *Aim 4:* To compare the interview and language interpretation quality and accuracy of Method A vs. Method B.
- *Aim 5:* To evaluate the diagnostic accuracy of facial recognition software compared with the psychiatrists

This highly innovative proposal builds logically on our prior feasibility studies and our current randomized clinical trial. The potential impact of this study is far-reaching if we find automated asynchronous language interpretation to be an improved, more easily accessible method of clinical interpretation that is acceptable to, or preferred by, LEP patients than in-person interviews. The automated translation approach we are using has the potential to dramatically expand clinical capacity nationally and worldwide by reducing the need for on-site interpretation services. We will be video recording all patients to collect their language and will use the facial interview data to examine the diagnostic accuracy of facial recognition software. While we are testing and evaluating our approach with Spanish-speaking patients in the field of psychiatry, this technical approach can be generalized towards primary care and other medical disciplines and could be applied to many other languages, as well as beyond the healthcare field.

4) Inclusion and Exclusion Criteria

We will only recruit Hispanic individuals with significant LEP — a critically underserved population — comprising 5% of the local Hispanic population at the Sacramento County Adult Psychiatric Support Services (APSS) Clinic and other Northern California mental health and primary care clinics. To help reach more a broader Spanish speaking population, we will also provide flyers to additional organizations (e.g. faith-based, social services, and etc.) that predominantly work with Spanish speaking individuals. Finally, we will be placing advertisements in both web based media (online journal) and paper based media (e.g. local

A clinical trial to validate an automated online language interpreting tool with Hispanic patients who have limited English proficiency – Phase Two.

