- The Clinical Global Impression – Severity scale (CGI-S)^{xxvi} is a 7-point scale that requires the clinician to rate the severity of the patient's illness at the time of assessment, relative to the clinician's past experience with patients who have the same diagnosis. The analogue scale that is routinely used by UCD psychiatrists as an outcome measure ranges from 1 (Normal) to 7 (Extremely ill, and likely to be an inpatient).
- Global Assessment of Functioning (GAF) used by clinicians to rate patients' social, occupational and psychological functioning.

The satisfaction and interview comparison measures will be:

- Patient Telepsychiatry Satisfaction Questionnaire. The provider questionnaire was used in our preliminary studies. The patient questionnaire is a modified version of the Parent Telemedicine Satisfaction Survey.^{xvi}
- Patients will report their perceived quality of the interpretation using a modified version of a UC San Francisco-developed tool measuring satisfaction of patient-centered tools through of quality of communication and visit satisfaction. These questions include the 4-item Quality of Interpretation Scale and the 4-item Patient Engagement Scale
- Patients will be asked to quantify on a number of visual analogue rating scales of 0-10 the two interview methods in terms of their likeability and effectiveness, using questions developed using the STAR technique^{xvii} (Situation, Task, Action, Result) which assess the effectiveness of the interview process in the recruiting sector.

The satisfaction, quality of interpretation and interview comparison questions have been integrated into a single document which all patients will complete in 3 components (Attached English and Spanish versions), after each of the interviews separately, and then after the second interview to enable comparison.^{xviii xix, xx, xxi}

The questionnaires, self-report measures and interviews will be conducted in person by our trained clinic provider in Spanish. The clinical functioning CGI and Global Assessment Of Functioning GAF will be completed by the interviewing psychiatrist [name]. We will also assess how clinicians and the care delivery systems work to help LEP patients make the best decisions about their health care. Specifically, we will assess

- provider diagnostic accuracy, inter-rater reliability and other psychiatrist related clinical outcome measures using Kappa as in our previous research¹¹

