Our anticipated sample size (100 patients, 50 per group) in this two-period cross-over study will allow us to achieve our descriptive and analytic aims with appropriate statistical power. We specified that the study should provide us at least 80% power under standard testing conditions (two-sided, with a type-1 error rate of 5%) and performed sample size computations using SAS power and sample size procedure PROC POWER. For Aim 2, assuming a range of within-subject correlation of 0.3-0.6 for the primary outcome (summary measure of patient satisfaction (based on overlapping questions for method A and B questionnaires) measured twice, after each assessment) we would have 80-96% power to detect a 0.33 SD difference in satisfaction levels between Method A and Method B, a small effect size.

A clinical trial to validate an automated online language interpreting tool with Hispanic patients who have limited English proficiency – Phase Two.

Figure 1. Outcome Comparison of 2 Interview Methods Study Design

8) Data and/or Specimen Management and Confidentiality

Federal clinical and research guidelines will be followed regarding screening, advertising, informed consent, confidentiality, and privacy issues. All procedures will be approved by the UC Davis Institutional Review Board (IRB) prior to implementation. We are not collecting any human specimens and are not performing any clinical intervention in this study. Data analysis is discussed above under “Procedures involved”.

9) Data and/or Specimen Banking

Our Internet-based system is fully HIPAA compliant and will be utilized to collect and manage multimedia and numeric data in this study. Data will be held in the same HIPAA compliant manner as for our UCD IRB approved trial 522696 “A controlled trial of Patient Centered Telepsychiatry Interventions” submitted 10-17-2013. The data will also reside on HIPAA-compliant Microsoft Azure instance, managed by UC Davis Health IT personnel, and all data

A clinical trial to validate an automated online language interpreting tool with Hispanic patients who have limited English proficiency – Phase Two.

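### Does a two-sided test of difference leave the plan unable to conclude that Method B is acceptable to patients?

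*Combined protocol and SAP*

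**What the plan says.** Section 3 (Background) of the combined protocol and SAP gives Aim 2 as "To compare patient satisfaction of Method A vs. Method B". It states no hypothesis of superiority, non-inferiority or equivalence. Later in the same section, a paragraph on potential impact says the consequences would be large if the automated method turned out to be an improvement, easier to access, and "acceptable to, or preferred by, LEP patients than in-person interviews". Method A is described as the current gold standard.

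Section 6 (Study Endpoints) lists the satisfaction measures: a telepsychiatry satisfaction questionnaire, two 4-item scales on interpretation quality and engagement, and 0-10 ratings of how likeable and effective each method is. Patients answer after each interview, and again after the second so that the two can be compared. No threshold is attached to any of these.

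Section 7 (Procedures Involved, Data Analysis) says "We specified that the study should provide us at least 80% power under standard testing conditions", which it defines as two-sided with a 5% type 1 error. For the satisfaction summary score, with a within-subject correlation of 0.3 to 0.6, it concludes that "we would have 80-96% power to detect a 0.33 SD difference in satisfaction levels between Method A and Method B".

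**The concern.** Section 3 names two welcome outcomes, preferred and acceptable, and the described test serves only the first directly. A two-sided test can show that Method B is liked more or liked less. If it shows neither, that does not establish that Method B is acceptable. On a natural reading, with Method A as the reference standard, acceptable means not worse by more than some tolerable amount, and the plan names no such amount.

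The fear is a non-significant result being written up as evidence that patients accept the asynchronous method while the data still allow a sizeable deficit. Because Section 3 links the value of the work partly to acceptability, a missing criterion looks like a mismatch between the conclusion sought and the test planned.

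**Working it through.** **Inputs.** From Section 7: 100 patients, each assessed by both methods (100 pairs); two-sided 5%; correlation ρ from 0.3 to 0.6; difference 0.33 SD. The documents give no margin, so any margin M below is an assumption shown over a range.

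**Step 1: the plan's own power.** In units of the SD of one measurement, the standard error of the mean paired difference is SE = √(2(1−ρ)/100).

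- ρ = 0.3: SE = √0.014 = 0.1183. Normal approximation: 0.33/0.1183 − 1.96 = 0.83, power 79.7%. Noncentral t, 99 df: 78.9%.
- ρ = 0.6: SE = √0.008 = 0.0894. Normal approximation: 0.33/0.0894 − 1.96 = 1.73, power 95.8%. Noncentral t: 95.5%.

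The stated 80-96% reproduces as a paired test of difference. A parallel comparison of 50 with 50 would give only 37.8%, so the paired structure is clearly what was used.

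**Step 2: what a non-significant result leaves open.** The half-width of the 95% confidence interval is h = 1.984 × SE. The interval's lower limit depends on the observed difference.

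| | ρ = 0.3 | ρ = 0.6 |
|---|---|---|
| h | 0.235 SD | 0.177 SD |
| Deficit unexcluded if the observed difference is 0 (= h) | 0.235 SD | 0.177 SD |
| Deficit unexcluded at the edge of significance (= 2h) | 0.470 SD | 0.355 SD |
| Largest observed deficit that still excludes 0.33 SD (= 0.33 − h) | 0.095 SD | 0.153 SD |

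The 2h row exceeds 0.33 SD at both ends, but this is nearly automatic. Under the normal approximation 2h is 3.92 SE, while the design effect is (1.96 + z) SE, where z is the normal quantile of the power. The first exceeds the second whenever z is below 1.96, that is, whenever power is below 97.5%. Almost any conventionally powered trial has this property.

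**Step 3: how often it would happen.** The probability that a result is non-significant and also fails to exclude a 0.33 SD deficit is P(−h < D < h − 0.33), where D is the observed difference, taken as normal.

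- Methods truly equal: 18.7% (ρ = 0.3), 2.0% (ρ = 0.6).
- True deficit 0.20 SD: 42.8% (ρ = 0.3), 10.3% (ρ = 0.6). The chance of any non-significant result here is 61% and 40%.

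**Step 4: what a margin would give.** Power for the lower 95% limit to lie above −M when the methods are truly equal, at ρ = 0.3 and 0.6:

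- M = 0.33 SD: 78.9%, 95.5%
- M = 0.25 SD: 55.3%, 79.0%
- M = 0.20 SD: 38.7%, 60.0%

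At M = 0.33 SD this matches Step 1 to the precision shown. If the sponsor did want a margin equal to the design effect, the existing sample would serve it about as well as it serves the present test.

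**The case for a change.** The strongest case for a change is that Section 3 is the only place that says what satisfaction result is hoped for, and half of that hope has no criterion. If acceptable is relative, a margin is missing; if it is absolute, a score cut-off is missing. A confidence interval read afterwards without a margin can be called acceptable by anyone. The cost of repair would be small: one sentence, or deletion of two words.

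Some of this stands. The documents contain no criterion on either reading, and a null result would not demonstrate acceptability. The chance of an ambiguous result is not negligible if Method B is truly somewhat less liked and the correlation is low.

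But the harm needs a step that the documents do not take, namely treating a non-significant difference as acceptability. The wording at issue is a conditional comment on impact, not an aim, endpoint or hypothesis, and the same paragraph also rests impact on clinical capacity and on extension to other disciplines and languages. A significant result for Method B would support acceptability as well as preference, so the gap is confined to null or mildly unfavourable results. Any margin would be a judgement for the sponsor that nothing in the documents fixes. Recruitment was due to start in October 2017 and this version is dated April 2019, so a margin chosen now might follow data already accrued.

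**Conclusion.** The observation is correct but calls for no change. The aim is a comparison, the test is a comparison, and the power figure is right for it. Following the plan as written gives a sound answer to Aim 2. The undefined term is a gap that analysts fill by ordinary good practice: report the 95% confidence interval for the B − A difference and do not describe a non-significant difference as acceptability.

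With 100 pairs that interval is reasonably informative. An observed difference of zero would exclude deficits beyond 0.18 to 0.23 SD. The 0.35 to 0.47 SD figure applies only to an estimate at the edge of significance, where no careful reader would claim acceptability.

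These sizes assume 100 complete pairs, roughly normal differences and a correlation between 0.3 and 0.6. The conclusion rests on acceptability remaining a Background remark. If the sponsor later wished to make it a formal finding, a margin or cut-off would have to be justified without sight of the outcome data, and the power restated.
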